6.6.4 Vital Signs and Physical Examinations

Height from the screening visit, weight, BMI, waist and hip circumference and vital signs (temperature, pulse, and respiratory rate) and change from baseline values in applicable follow-up visits will be presented in data listings by subject.

Summaries of observed height, weight, BMI and vital signs of observed values and changes from baseline will be presented by Randomized Sequence and in total for each applicable follow-up visit.

A table will summarize physical examination results by Randomized Sequence and in total. The summary will include the number and percentage of participants with physical examination outcome (Normal, Abnormal [Not Clinically Significant, Clinically Significant])

In addition, the number and percentage of subjects who experienced a ≥20 bpm increase from baseline in pulse will be summarized. In these summaries, the first occurrence of the event per subject will be summarized. Investigator assessment of body system (Normal, Abnormal) performed during the complete physical examination will be listed but not summarized.

6.6.5 12-Lead Electrocardiogram (ECG)

ECG results (PR, RR, QRS, QT, QTcB, QTcF, and overall ECG evaluation [Normal, Abnormal not Clinically Significant, Abnormal Clinically Significant]) will be presented in data listings by subject and visits.

6.6.6 Prior and Concomitant Medications

Prior medications are defined as any medications taken and stopped prior to the start of the study drug (including prior to run-in period).

Concomitant medications are defined as any medication or vaccine (including over the counter medications, prescription medications, recreational drugs, vitamins, and/or herbal supplements) with a start date on or after the first study investigational drug administration (following randomization) or medications with a start date prior to first study investigational drug administration but ongoing or with stop dates on or after first study drug administration. Medications that stop during the run-in period will be considered prior medications. Medications with a start date after the last study drug administration will not be considered as concomitant medications; these post-treatment medications will be identified in the listing.

The number and percentage of subjects with concomitant medications will be summarized by WHO-DD Anatomical-Therapeutic-Chemical 2 (ATC2) classification and PT by treatment sequence group and treatment period and in total. The summary table will display counts and percentages of subjects who reported using at least 1 concomitant medications in any of the treatment groups in each treatment period. Subjects may have more than 1 medication per ATC2 classification. At each level of subject summarization, a subject will only be counted once if he/she reports 1 or more medications.

A similar summary table will be created for rescue medication data. Rescue medications are defined as any new anti-hypertensive treatment that starts between the first administration of the double-blind study drug and either the last administration of the double-blind study drug or the AOBP assessment at week 12, whichever occurs later. Replacement of Antihypertensive therapy (AHT) medication in the prescribed AHT regime with equivalent medication from the same class will not be considered a rescue medication. Change in dose will not be considered a rescue medication. Time from baseline to initiation of rescue medication will be analyzed by treatment group using Kaplan-Meier methods. Subjects without rescue medication by Week 12/EoT will be censored on this date.

Only concomitant and rescue medication data will be summarized but a listing of all prior, concomitant, and post-treatment medication data will be provided.

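### The rescue-medication Kaplan-Meier runs one clock from baseline to Week 12 across both drugs and the washout, and the pulse-outlier and physical-examination summaries have no period or drug attribution

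*SAP*

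**What the plan says.** On rescue, SAP 6.6.6 states: "Time from baseline to initiation of rescue medication will be analyzed by treatment group using Kaplan-Meier methods". The next sentence sets one censoring date: "Subjects without rescue medication by Week 12/EoT will be censored on this date". The definition of rescue in the same section covers new antihypertensive treatment from the first double-blind dose to the last such dose or the Week 12 AOBP, whichever is later, so starts during washout count. The section also plans a count table, "A similar summary table will be created for rescue medication data", modelled on the concomitant-medication table, which is laid out by ATC2 "classification and PT by treatment sequence group and treatment period and in total".

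In SAP 6.6.4, vital-sign summaries "will be presented by Randomized Sequence and in total for each applicable follow-up visit". The physical-examination table is by randomized sequence and total, with no visit or period named. For the outlier count, "the number and percentage of subjects who experienced a ≥20 bpm increase from baseline in pulse will be summarized", and "the first occurrence of the event per subject will be summarized". No grouping is given for that count.

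Four other provisions bear on this. SAP 5.2 defines treatment arm as lorundrostat or placebo and says each subject is planned to receive both. SAP 6.2.2 makes the pre-TP1 value the default baseline for non-efficacy data, with TP1 and TP2 baselines when a change relates to the crossover design. SAP 5.5.2 leaves open whether vitals will be organised by crossover. SAP 6.6.1 allocates safety events from Week 0 to Week 8, washout included, to the first drug, and later events to the second; it gives a display layout only for AEs.

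**The concern.** A single origin and a single end date suit a parallel-group trial, where a subject has one treatment throughout. Here, 12 weeks of follow-up contain four weeks of lorundrostat, four of washout and four of double-blind placebo, and the two sequences differ only in order. The SAP does not say how a subject who belongs to both treatment groups enters the curves.

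The stake is the reading of the blood-pressure result and of safety. Table 5 of the SAP lists only permanent discontinuation and death as intercurrent events, and its footnote says changes to background antihypertensives do not qualify. Blood pressure after rescue therefore enters the primary analysis as observed, and the rescue outputs are where a reader would look to see whether rescue differed by drug. The documents do not themselves describe rescue as a check on the primary result; that is my reading. Heart rate and physical examination are named safety endpoints in Protocol 3.2.3.

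**Working it through.** The documents give no rescue or pulse-event rates and no figure to reproduce. All risks below are assumptions, chosen to show structure.

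**1. Rescue curves drawn by sequence.** Let pL, pW and pP be the four-week risks of starting rescue, among subjects not yet rescued, on lorundrostat, in washout and on double-blind placebo. Week 12 incidence is

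- LP: 1 − (1 − pL)(1 − pW)(1 − pP)
- PL: 1 − (1 − pP)(1 − pW)(1 − pL)

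The product does not depend on order, so the two are equal for any pL. This needs no period or carryover effect and the same pW in both sequences. With pW = pP:

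| pP / pL | LP at Weeks 4, 8, 12 | PL at Weeks 4, 8, 12 |
|---|---|---|
| 5% / 2% | 2.0, 6.9, 11.6% | 5.0, 9.8, 11.6% |
| 10% / 4% | 4.0, 13.6, 22.2% | 10.0, 19.0, 22.2% |
| 20% / 8% | 8.0, 26.4, 41.1% | 20.0, 36.0, 41.1% |

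For the middle row, 1 − (0.96)(0.90)(0.90) = 0.2224 in both sequences. The curves do separate in Weeks 0 to 4, and only that segment is a clean comparison.

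Expected log-rank |Z|, with piecewise-constant hazards and 30 subjects per sequence (60 randomized 1:1):

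| pP / pL | By sequence to Week 12 | TP1 alone | Both periods, clock restarted |
|---|---|---|---|
| 10% / 4% | 0.08 | 0.91 | 1.29 |
| 20% / 8% | 0.25 | 1.34 | 1.90 |

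The last column uses 60 subject-periods per drug, treated as independent. The SAP specifies no rescue test; the Z values only show how much of the contrast each display keeps.

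**2. Rescue curves drawn by drug.** In PL, lorundrostat starts at Week 8. With time measured from baseline, a PL subject on the lorundrostat curve carries eight weeks of risk time before the first lorundrostat dose. An LP subject carries eight weeks after the last one. So 8 of 12 weeks on that curve are off lorundrostat. If washout starts were allocated as in SAP 6.6.1, then at 10% / 4%:

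- lorundrostat receives 30 × 0.04 = 1.2 TP1 starts plus 30 × 0.96 × 0.10 = 2.88 washout starts, or 4.08 of 30 (13.6%);
- placebo receives 30 × 0.10 = 3 plus 30 × 0.90 × 0.10 = 2.7, or 5.7 of 30 (19.0%).

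An assumed risk ratio of 0.40 would read as 13.6 / 19.0 = 0.72 at Week 8.

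**3. Pulse rise of 20 bpm or more.** Assume 15% per period on lorundrostat, 5% on placebo, and independent periods.

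- Per subject, by sequence: 1 − (0.85)(0.95) = 19.25% in both LP and PL.
- By drug, first occurrence only: lorundrostat (0.15 + 0.95 × 0.15) / 2 = 14.6%; placebo (0.05 + 0.85 × 0.05) / 2 = 4.6%.

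More generally, if x is the chance of an event in both periods, each by-drug rate falls by x/2. With equal sequences and no period effect the difference between drugs is kept. The loss is serious if the count is by sequence or in total, and modest if it is by drug.

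**4. Vital signs.** The sequence-by-visit cells identify the drug: LP at Weeks 2 and 4 and PL at Weeks 10 and 12 are lorundrostat. The contrast is ½[(LP4 − PL4) − (LP12 − PL12)], and a single baseline cancels. In a test case with a true effect of 4, mean changes of +3 and −2 in LP and −1 and +2 in PL give ½[(3 + 1) − (−2 − 2)] = 4.

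**The case against.** A reader might infer that SAP 6.6.4 and 6.6.6 as a whole cannot tell lorundrostat from placebo. The documents do not support that. The rescue count table is by sequence and period, so each treatment-period cell identifies the drug. Vital signs are by sequence at each visit, and step 4 recovers the contrast exactly; that table lacks only a treatment column and a within-subject standard error, and its total column mixes drugs. SAP 6.2.2 also allows period baselines. These points stand, and vital signs are not part of the fault.

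It can also be said that the Kaplan-Meier is specified by treatment group, not by sequence, so equal Week 12 values describe a display the SAP does not name. That is fair, but the by-drug reading fails in another way (step 2), and SAP 6.6.1 does not mend it: it sets no clock and charges placebo washout to the first drug.

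For pulse, the SAP names no grouping, and SAP 6.6.1 could be read as assigning events to drug. If so, the distortion is small under independence. The count is then underspecified, but a TP1 event still removes the subject's TP2 event on the other drug.

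Finally, rescue events may be few: at 10% / 4%, about 1.2 + 3 = 4.2 starts are expected in TP1. That argues for a descriptive display.

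**Conclusion.** The concern holds for three outputs. The rescue Kaplan-Meier, followed as written, gives no valid 12-week comparison of the drugs under either reading of treatment group. By sequence, the Week 12 difference is zero whatever the drug effect, given no period or carryover effect and equal washout risk; by drug, risk time is misdated. The pulse count needs a period and a grouping, and the physical-examination table needs a period or visit and a treatment column. The sizes rest on assumed risks, but the equality at Week 12 does not depend on which risks are chosen.

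It does not extend to vital signs or to the rescue count table, where drug can already be identified, and it does not touch the primary test. These are descriptive outputs, so the change should be made but is not critical.

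**What to change.** **Rescue Kaplan-Meier.** Start the clock at the first dose of each treatment period, count new antihypertensive treatment up to that period's Week 4 AOBP, censor there, and group by the drug of that period. Show TP1 alone, then both periods by treatment, as description. Tabulate washout starts, and rescue carried into TP2, separately. Do not exclude subjects from TP2 because of rescue in TP1: that would condition on a post-randomization outcome that may depend on the TP1 drug.

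**Pulse and physical examination.** Count the pulse outlier once per subject per period against that period's baseline. Show it and the physical examination by treatment within period and treatment total, the layout the SAP already uses for AEs and laboratory data.

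**Vital signs.** The same by-treatment summary can be added for consistency only.

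The cost is a few sentences in SAP 6.6.4 and 6.6.6, revised shells and programming. No new data are needed.

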6.6.6.1 Imputation of Missing Data for Concomitant Medications

Partial dates entered in the CM form will be imputed for the purposes of determining whether the record is a concomitant or prior medication based on the following:

- Medications that are not ongoing and have a medication stop date with a missing day and non-missing month will be assumed to occur on the last day of the non-missing month.
- Medications that are not ongoing and have a medication stop date with missing day and month will be assumed to occur on the last day of the non-missing year (i.e., December 31).
- Partial or missing CM start dates will be imputed as follows:
 - Missing day will be imputed as the first day of the month.
 - Missing month will be imputed as January.

7 CHANGES TO PLANNED ANALYSES

There were no changes between the protocol-defined statistical analyses and those presented in this statistical plan.

9 APPENDICES

9.1 Schedule of Assessments

Study Period	Screening ¹	Run-in	Randomization ²	Treatment Period 1 (4 weeks)		Wash Out (4 weeks)	Treatment Period 2 (4 weeks)		EoS ³	Unscheduled Visit ⁴
Weeks ⁵	-4	-2	0	2	4	8	10	EOT 12	14	UNS
Study Visit#	1	2	3	4	5	6	7	8	9	
Informed Consent ⁶	X									
Randomization			X							
Demographics	X									
Medical history	X									
Eligibility confirmed	X		X							
Concomitant medications	X	X	X	X	X	X	X	X	X	X
Physical exam, body weight, height, waist and hip circumference ⁷	X		X	X	X	X	X	X	X	X
Vital signs	X	X	X	X	X	X	X	X	X	X
AOBP, seated and standing	X		X	X	X	X	X	X	X	X
12-lead ECG	X		X						X	X
Serum chemistry (including eGFR, excluding potassium) central lab	X		X	X	X	X	X	X	X	X
Cystatin-C (central lab)	X		X	X	X	X	X	X	X	X
Serum potassium (local lab)	X		X ⁸	X	X	X	X	X	X	X
HbA _{1c} (central lab)	X				X			X	X	X
Hematology (central lab)			X		X			X	X	X
Urinalysis, spot urine (central lab)	X				X			X	X	X
Dispense kit for first morning urine void	X	X		X			X			X
Subject collects first morning urine void, midstream ⁹	X		X		X			X		X
Dispense kit, for 24-hour urine ¹⁰	X	X		X	X		X			X
Subject collects 24-hour urine ¹¹		X	X		X	X		X		X
Pregnancy test ¹²	X		X			X		X	X	X
Adverse events ¹³	X	X	X	X	X	X	X	X	X	X
Study drug dispensed		X ¹⁴	X		X	X				X
In-clinic dosing			X	X	X	X	X	X		X
Study drug compliance			X	X	X	X	X	X	X	X
Biomarkers (central lab) ¹⁵			X		X	X		X	X	X
Morning serum cortisol ¹⁶	X			X	X		X	X		X
PK (sampling) ¹⁷				X	X		X	X		
ACTH stimulation test ¹⁸										X

- 1 Screening will be 2 weeks. However, if required, the screening window may be extended to 4 weeks without approval from the Medical Monitor.
- 2 Only subjects who continue to meet all eligibility criteria will be randomized.
- 3 Visit for subjects not participating in the open label extension study only. Study visit window is \pm 5 days.
- 4 Assessments performed during an unscheduled visit will be done on an as needed basis.
- 5 Study visit windows (double blind period and run-in) are \pm 3 days.
- 6 Written informed consent must be obtained prior to conducting any study procedures.
- 7 At the Screening Visit a physical examination will be performed and should include an evaluation of the cardiovascular, dermatologic, musculoskeletal, respiratory, gastrointestinal, and neurologic systems. Height will be measured at Screening only. At other visits, a limited, symptom-directed physical examination should be performed. Any abnormality identified should be recorded either as medical history or AE accordingly.
- 8 Serum potassium must be collected 3 days prior to Randomization and values must be reviewed by the Investigator for Randomization eligibility.
- 9 During Screening, one first morning urine void to be brought in, in the first week after Screening to determine eligibility. An unscheduled visit during Screening period for subjects to return first morning void must take place a minimum of 7 days prior to the Run-in visit so that the result is available for eligibility review. The sample needs to be 200-5000 mg/g inclusive to meet eligibility criteria. Samples will be assessed for albumin, protein, and creatinine.
- 10 Subjects will be given a 24-hour urine collection kit to take home at preceding visits. An aliquot of urine will be retained for future biomarker assessments.
- 11 Subjects must start urine collection on Day-1 and return the collected 24-hour urine on Week 0 Randomization visit. 24-hour urine samples will be utilized for assessment of albumin, protein, creatinine, sodium, potassium, cortisol, and aldosterone. An aliquot of urine will be retained for future assessments.
- 12 Women of childbearing potential only. A sample for serum pregnancy test will be collected at Screening. Follicle stimulating hormone must be used to confirm postmenopausal status in all postmenopausal women at Screening. Urine pregnancy tests will be done at other visits. If urine pregnancy test is positive, a serum pregnancy test will be collected to confirm results at the local lab.
- 13 All AEs and SAEs will be collected from signing of informed consent form until the subject has completed the EoS visit or transitioned to the open label extension study. All AESIs will be collected upon initiation of treatment until the subject has completed the EoS visit or transitioned to the open label extension study.
- 14 Only for SGLT2i naïve patient or patient switching to sponsor provided SGLT2i.
- 15 An aliquot of serum will be retained for future biomarker assessments. A sample of whole blood will be collected at Randomization and retained for future proteomic and genomic assessments. A mid-stream urine sample will also be collected for future biomarker analyses. Blood and urine samples will be processed and stored as described in the laboratory manual.
- 16 Blood draw for cortisol assessment should occur as close to 8 AM as possible on the morning of the study visit.
- 17 Subjects should have a blood sample drawn just prior to dosing and another blood sample taken 1-2 hrs. post-dose.
- 18 ACTH (Cosyntropin) stimulation testing to be performed at unscheduled visits if clinically indicated by signs, including serum cortisol below 3 μ g/dL, or below 10 μ g/dL accompanied by symptoms of hypocortisolism.
